G. Exploratory Research Hypotheses

1. Blood periostin (or other biomarkers such as blood eosinophils, or eNO) will be as effective as sputum eosinophils at identifying patients likely to respond to ICS.

2. The Asthma Index, together with associated questionnaires, will characterize the time course and magnitude of morbidity associated with asthma exacerbations and serve as a tool for studying interventions for management of asthma exacerbations.

3. Among asthmatic participants who are persistently non-eosinophilic, the preference for ICS is not greater than for LMA.

4. Among asthmatic participants with sputum eosinophilia, the preference for ICS is greater than for LMA.

H. Primary Outcome Measure

The primary outcome is a hierarchical composite of three measures of asthma control, assessed during the last 8 weeks of each 12 week treatment

period: Treatment Failure (TF), Asthma Control Days (ACD), FEV₁.

The definition of **TF** comes from the Symptom-Based Action Plan that was utilized successfully in the ACRN IMPACT Study ³ and includes:

- Awakening from asthma three or more times in a two-week period or on two consecutive nights, or
- Using albuterol for relief of symptoms four or more times/day for two or more consecutive days, or
- Albuterol has been relieving symptoms for less than four hours after each treatment over a 12-hour period, or
- Using albuterol for relief of symptoms daily for seven days, and this use exceeds two times the weekly use of albuterol in the baseline period, or
- exercise induces unusual breathlessness.

ACDs will be documented in daily diaries, and are defined as: A day with no rescue albuterol use (pre-exercise albuterol will not be counted), no non-study asthma medications, no daytime asthma symptoms (shortness of breath, wheezing, chest tightness, phlegm/mucus rated as mild, moderate or severe, or cough rated as moderate or severe), no nighttime asthma symptoms, no unscheduled healthcare visits for asthma, and no PEF < 80% of predetermined baseline.

FEV₁ is a standard outcome measure for asthma, and was used in a similar hierarchical preference analysis in BADGER¹⁸.

I. Secondary Outcome Measures

Each of the three components of the composite outcome (TF, ACD, FEV₁) will be analyzed separately as secondary outcomes. Other secondary outcomes include PEF, asthma exacerbations, time to treatment failure and time to first exacerbation.

J. Exploratory Outcome Measures

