treatment phase. Based on a “cut point” of $\geq 2\%$ eosinophils and two measures of sputum eosinophil % during the Run-in, participants will be categorized as “eosinophilic” (either persistently or intermittently), EOS+, or “persistently non-eosinophilic”, EOS-, and stratified on this basis at randomization. Initially, sites will recruit and randomize all eligible participants, and not be restricted to a specific distribution of eosinophil positive and eosinophil negative. Based on our prior ACRN experience with this very mild population, we anticipate that the distribution of eosinophil negative and eosinophil positive participants will be $\leq 3.5:1$ at each site. The DCC will monitor enrollment and may subsequently restrict enrollment if necessary to create balanced accrual.

[figure not shown]
D. Double-Blind Treatment Period

Each treatment arm will be 12 weeks in duration without formal washouts; data from the first 4 weeks of each treatment period will be censored. Participants will be seen every 6 weeks for the duration of the study (9 visits total) and will be assessed by phone call at the 3-week point between visits. All participants will continue their electronic diaries throughout the study. At the time of randomization and at the end of each treatment period, participants will have an interim history, diary review, spirometry, and will complete questionnaires to assess asthma symptoms, asthma control, and quality of life. Treatment Failure status will be defined and treated as in the Run-In. Participants who experience ≥ 2 Treatment Failures or an Asthma Exacerbation will cross over to the next treatment arm (or have their final visit should this occur during the final treatment period). Participants who experience an Asthma Exacerbation will be treated with

prednisone and seen at the clinic after 3 days to ascertain the severity of the event and ensure appropriate treatment. Spirometry will be performed. During periods 1 and 2, this clinic visit will coincide with their crossover visit and during period 3, this visit will coincide with their final in-person visit. Phone visits will be conducted on days 10, 14, and 21 following prednisone start to monitor exacerbation recovery, and additional safety visits will occur if necessary.

[figure not shown]
E. Characterization of Asthma Exacerbations

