Because SIENA invokes a three-way crossover design, a stratified randomization based on prognostic factors is not critical. Instead, we only will invoke clinical site within phenotype (eosinophilic, non-eosinophilic) as a stratifying variable with permuted blocks of size six (one complete cycle of the six sequences). When a participant at a particular Clinical Center is deemed eligible for the study, the Clinic Coordinator will access the AsthmaNet Randomization Module. After entering the participant's pertinent information, the Clinic Coordinator will be asked to verify that all of the entered information is correct. If so, the Clinic Coordinator will be given inhaler numbers to be dispensed to that participant. At certain visits, the coordinator will access the Randomization Module again to generate new inhaler numbers containing the regimen consistent with the participant's randomized drug sequence. In order to maintain security of the randomization schedules, DCC data management and

coordination staff will receive automatically a notice from the AsthmaNet server that a participant has been randomized and/or had a new inhaler number generated.

B. Masking

To minimize the bias due to possible knowledge of the sequence assignment, the study will be double-blinded. Thus, the investigators and the participants will not know which treatments are being administered during the treatment periods.

C. Statistical Analysis Plan for the Primary and Secondary Outcomes

The SIENA trial invokes a three-way crossover design. Each of the three treatment periods endures for 12 weeks, but the data from the first four weeks of each treatment period are not used in the statistical analyses because of the lack of wash-out periods in the crossover design.

The primary outcome in the SIENA trial is a composite based on the three components of treatment failure, asthma control days (ACDs), and FEV₁. For each SIENA participant, we will compare ICS to placebo and LMA to placebo in a hierarchical manner based on the data from the latter eight weeks of their respective treatment periods. The process is described as follows for the generic comparison of treatment regimen A to treatment regimen B:

1. If the SIENA participant does not experience treatment failure on treatment regimen A, but does experience treatment failure on treatment

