regimen B, then treatment regimen A is deemed to be superior to treatment regimen B and the process is terminated. If not, then continue to the next step.

2. If the SIENA participant experiences at least 31 greater annualized ACDs on treatment regimen A as compared to treatment regimen B, then treatment regimen A is deemed to be superior to treatment regimen B and the process is terminated. If not, then continue to the next step.

3. If the SIENA participant displays at least a 5% improvement in FEV₁ on treatment regimen A as compared to treatment regimen B, then treatment regimen A is deemed to be superior to treatment regimen B and the process is terminated. If not, then the two treatment regimens are deemed to be “equivalent” or “tied” for that SIENA participant.

In order to describe the primary and secondary null hypotheses, we introduced the following notation:

- $p_{Eos-,ICS>Placebo}$ = probability that ICS is superior to placebo within the non-eosinophilic phenotype
- $p_{Eos-,Placebo>ICS}$ = probability that placebo is superior to ICS within the non-eosinophilic phenotype
- $p_{Eos-,ICS\approx Placebo}$ = probability that ICS and placebo are equivalent within the non-eosinophilic phenotype = $1 - p_{Eos-,ICS>Placebo} - p_{Eos-,Placebo>ICS}$
- $p_{Eos-,LMA>Placebo}$ = probability that LMA is superior to placebo within the non-eosinophilic phenotype

- $p_{Eos-, Placebo > LMA}$ = probability that placebo is superior to LMA within the non-eosinophilic phenotype
- $p_{Eos-, LMA \approx Placebo}$ = probability that LMA and placebo are equivalent within the non-eosinophilic phenotype = $1 - p_{Eos-, LMA > Placebo} - p_{Eos-, Placebo > LMA}$
- $p_{Eos+, ICS > Placebo}$ = probability that ICS is superior to placebo within the eosinophilic phenotype
- $p_{Eos+, Placebo > ICS}$ = probability that placebo is superior to ICS within the eosinophilic phenotype
- $p_{Eos+, ICS \approx Placebo}$ = probability that ICS and placebo are equivalent within the eosinophilic phenotype = $1 - p_{Eos+, ICS > Placebo} - p_{Eos+, Placebo > ICS}$
- $p_{Eos+, LMA > Placebo}$ = probability that LMA is superior to placebo within the eosinophilic phenotype
- $p_{Eos+, Placebo > LMA}$ = probability that placebo is superior to LMA within the eosinophilic phenotype
- $p_{Eos+, LMA \approx Placebo}$ = probability that LMA and placebo are equivalent within the eosinophilic phenotype = $1 - p_{Eos+, LMA > Placebo} - p_{Eos+, Placebo > LMA}$

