Participants who develop treatment failure during the Run-In period or double-blind Treatment Period will be treated as described previously with high-dose ICS (i.e., mometasone 400-440 mcg BID, dose dependent on mometasone device randomized to at Visit 3 – See Appendix D x 10 days), and continue in the study. Participants who experience two treatment failures during the run-in period will not be allowed to participate in the study further. Participants who meet criteria for treatment failure during the double-blind Treatment Period will continue in the study. If the treatment failure occurs <3 weeks before the end of

a treatment period, that period will be extended so that ≥ 3 weeks will have elapsed before the participant crosses over to the next treatment arm (or has their final visit should this occur during the final treatment period). Participants who experience ≥ 2 Treatment Failure episodes or an Asthma Exacerbation during a treatment arm will cross over to the next treatment arm (or have their final in-person visit should this occur during the final treatment period).

Participants who experience a treatment failure event that also meets the criteria for an asthma exacerbation, will be treated with Prednisone. For both adults and children, the recommended prednisone dose for acute exacerbations is 2 mg/kg/day (maximum 60 mg) as a single morning dose for three days followed by 1 mg/kg/day (maximum 30 mg) as a single morning dose for 2 days; all administered doses will be rounded down to the nearest 5 mg in children. Participants will be assessed in person and by phone on days 0, 3, 10, 14, and 21. Additional visits and treatment for exacerbations is at the discretion of the treating physician.

E. Rescue Algorithm for Asthma Exacerbations and Treatment Failure Non-responders

Participants who are not responsive to the treatment failure rescue algorithm or those who develop asthma exacerbations will be managed according to the following rescue algorithms. Rescue algorithms are based on recommendations from the NAEPP Guidelines for Diagnosis and Management of Asthma and prior ACRN trials. Albuterol and oral prednisone are the principal medications for rescue management and participants will be instructed in their

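### The primary hierarchy has no valid score for a treatment period ended in weeks 1-4 by an exacerbation or two treatment failures

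*Combined protocol and SAP*

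**What the plan says.** **Window.** III.H defines the composite as "assessed during the last 8 weeks of each 12 week treatment" period. VIII.C repeats this: each period lasts 12 weeks, "but the data from the first four weeks of each treatment period are not used in the statistical analyses", and the reason given is "because of the lack of wash-out periods in the crossover design". The sentence that introduces the three steps says the comparison is "based on the data from the latter eight weeks of their respective treatment periods".

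**Steps.** Step 1 reads "If the SIENA participant does not experience treatment failure on treatment regimen A, but does experience treatment failure on treatment" regimen B, in which case A is superior. Step 2 begins "If the SIENA participant experiences at least 31 greater annualized ACDs on treatment regimen A as compared to treatment regimen B". Step 3 asks for at least a 5% improvement in FEV1. If no step separates the arms the pair is tied, and tied participants are left out of the exact binomial test.

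**Ending a period.** IV.D says that participants with two or more "Treatment Failures or an Asthma Exacerbation will cross over to the next treatment arm", or have their final visit if already in period 3. X.D says the same: "Treatment Failure episodes or an Asthma Exacerbation during a treatment arm will cross over to the next treatment arm". VI.D agrees. None of these sections sets a minimum time on treatment. After an exacerbation the crossover coincides with the clinic visit 3 days later (IV.D, VI.D). X.C makes every exacerbation meet the TF criteria as well.

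**Only adjustment to period length.** VI.D and X.D extend a period when a TF falls less than 3 weeks before its end. No text says what to do with a period that has no data in weeks 5-12.

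**The concern.** TF is the top tier of the hierarchy. An exacerbation, or two TFs, within the first four weeks is among the worst results a participant can have on a regimen. It is also the result that the analysis window removes completely. Whether such a pair enters the primary test, and for which arm, would then be decided by an analyst's choice that the plan does not fix.

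The literal wording also goes beyond leaving a blank. It can produce a wrong ranking, because an arm abandoned in week 2 after an exacerbation has no TF inside the window, while an arm with one TF in week 9 does.

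Safety oversight is not at issue: the DSMB sees these events under VIII.F. The point concerns the two co-primary tests only.

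**Working it through.** **1. Following one pair through the rules.** Suppose the placebo period ends in week 2 with an exacerbation.
- Step 1: no placebo TF falls in weeks 5-12.
- Step 2: 0 of the 56 window days are observed on placebo, so annualised ACD has no denominator.
- Step 3: the clinic visits of a period fall at its weeks 6 and 12 (VI.E), so there is no scheduled in-window FEV1.
- Result: if the active arm has no TF in weeks 5-12, the pair is unscorable or tied. If it has one, step 1 ranks placebo superior.

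**2. Do other sections settle it?** The intention-to-treat sentence in VIII.C includes available data but gives no score to an empty window. VIII.E deals with drop-outs and missed visits under missing-at-random and relies on likelihood methods, whereas the primary test is an exact binomial test on preferences already formed. The contingent model in Appendix D has no scoring rule either.

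**3. The plan's own power.** Inputs from VIII.G: N = 262, 15% drop-out, 30% ties, difference 0.20, two-sided 0.025. Evaluable: 262 x 0.85 = 222.7, taken as 222. Win + loss = 0.70 and win - loss = 0.20, so win w = 0.45, loss l = 0.25, and the active share is 0.45/0.70 = 0.643. With non-tied pairs ~ Bin(222, w + l) and wins ~ Bin(n, w/(w + l)), exact power is 0.900. The plan's 0.90 is reproduced.

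**4. Illustration.** Let a be the fraction of pairs with an early exit on placebo only, and b on active only. Both are assumptions. The calculation also assumes that 0.45/0.25 credit early exits as failures.
- Fully informative loss: w = 0.45 - a, l = 0.25 - b.
- Loss unrelated to preference, with q = a + b: w = 0.45(1 - q), l = 0.25(1 - q).
- Literal step 1, assuming a share f = 0.20 of exit pairs has a week 5-12 TF on the other arm and the rest are tied: w = 0.45 - (1 - f)a + f b, l = 0.25 - (1 - f)b + f a.

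| a / b | pairs affected (222 x (a + b)) | informative | unrelated | literal step 1 |
|---|---|---|---|---|
| 1% / 0.5% | 3.3 | 0.891 | 0.895 | 0.888 |
| 2% / 1% | 6.7 | 0.880 | 0.890 | 0.873 |

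**5. Direction.** The active share is unchanged when a/b equals:
- informative loss: 0.45/0.25 = 1.8;
- literal step 1: setting (-0.8a + 0.2b)/(-0.8b + 0.2a) = 1.8 gives 1.64b = 1.16a, so a/b = 1.41;
- unrelated loss: any ratio, since the share never moves.

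Above the break-even ratio the active share falls; below it, it rises. At 5%/5% with fully informative loss, power rises to 0.944.

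**6. Periods shortened after week 4.** These do record an in-window TF if the ending event falls in the window. When the other arm has one too, the pair passes to steps 2 and 3. If annualised ACD means 365 x ACDs / observed days, one diary day is worth 365/56 = 6.5 on a full window and 365/11 = 33.2 on 11 days. With 11 or fewer days, a single day exceeds the 31-day threshold.

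**The case against.** **Step 1 carries no date limit of its own**, and TF is assessed throughout treatment, so an early TF might be meant to count. This reading is possible but weak: the sentence introducing the steps and the outcome definition in III.H both restrict the data to the last eight weeks.

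**The two-TF route is less certain than the exacerbation route.** No crossover time is given after a second TF. If the 3-week extension in VI.D and X.D also covers a period ended this way, a second TF in weeks 2-4 would leave some in-window data. This stands as a limit on the point. Even then, the failures themselves lie outside the window, so step 1 would still not count them.

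**The event may be rare.** V.D bars randomization after two or more Run-In TFs or any Run-In exacerbation. This also stands: no rate is given, and a low one is plausible.

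**The power losses may not be losses against the plan.** If 0.45/0.25 already describe the outcome as written, planned power stays at 0.90. VIII.G does not say which is meant, nor whether unscorable pairs fall within the 15% drop-out allowance.

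**The shortened-window issue is narrow.** It needs a TF on both arms. Because a visit is scheduled at week 6 of each period, an FEV1 available only from the exacerbation visit is confined to exits in about weeks 5-6.

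**Conclusion.** The gap is real and lies in the primary endpoint. The crossover rule and the analysis window collide, and nothing elsewhere in the plan resolves the collision. It is well supported for exacerbations and conditional for two TFs. It should be fixed.

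The size is not established. Under the assumed exit rates and the stated reading of 0.45/0.25, power is about 0.87 to 0.90 against 0.90, with roughly 3 to 7 pairs affected.

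A reader might infer that the trial is materially underpowered, or that the gap biases the result against active treatment. The documents support neither. A larger drop needs higher early-exit rates that nothing in the plan suggests. The direction depends on the ratio of placebo-only to active-only exits and on how the lost pairs would have scored. The 1.8:1 break-even belongs to fully informative loss alone; it is about 1.4:1 under literal step 1 with 20% other-arm TF, and there is none if loss is unrelated to preference.

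**What to change.** In III.H and VIII.C, before unblinding, state that:

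1. A period ended in weeks 1-4 by an exacerbation or two TFs is never scored as free of TF. It counts as TF at step 1. The week 1-4 exclusion stays for single TFs, ACD and FEV1.
2. If the other arm also has a TF and the shortened period has no in-window data, the pair is scored as tied.
3. As a secondary matter, when both arms have a TF and a period is shortened after week 4, a minimum number of in-window diary days applies to annualised ACD, and the spirometry that counts is named.

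Add two sensitivity analyses: (a) exclude periods ended in weeks 1-4; (b) count such exits in period 1 only. Making (a) the primary rule, with rule 1 as the sensitivity analysis, would also close the gap if stated in advance.

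The cost is plan wording and two analyses of data already collected. The real downside is carryover: weeks 1-4 are excluded because there is no washout, so in periods 2 and 3 rule 1 will charge some events caused by the previous arm to the new one. Analyses (a) and (b) show how far the result depends on this but do not remove it. No change to the crossover or rescue rules is proposed.

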For these reasons, we have chosen to compare inhaled corticosteroids to a long-acting muscarinic antagonist and to placebo in this study of non-eosinophilic asthma.

III. HYPOTHESES TO BE TESTED IN THIS TRIAL

A. Overall Research Question

Among asthmatic participants who are persistently non-eosinophilic (<2% sputum eosinophils in two induced sputum samples collected 3-6 weeks apart), is there a preference for inhaled corticosteroids (ICS) or long-acting muscarinic antagonist (LMA) compared to placebo?

B. Co-Primary Research Questions

1. Among asthmatic participants who are persistently non-eosinophilic, is there a preference for ICS compared to placebo?

2. Among asthmatic participants who are persistently non-eosinophilic, is there a preference for LMA compared to placebo?

(For both ICS and LMA, preference to treatment is defined as the following hierarchy of outcomes: Treatment Failure = TF, then Asthma Control Days = ACD, then FEV₁)

C. Secondary Research Question

1. Does the statistical preference for each of three alternative therapies (ICS, LMA, placebo) differ in participants with the non-eosinophilic phenotype compared with participants with sputum eosinophilia?

D. Exploratory Research Questions

1. Can other, easier to obtain biomarkers (blood periostin, blood eosinophils, or eNO) be used instead of sputum eosinophils to identify patients likely to respond to ICS?

2. Among asthmatic participants who are persistently non-eosinophilic, is there a preference for ICS compared to LMA?

3. Among asthmatic participants with sputum eosinophilia, is there a preference for ICS compared to LMA?

4. When do patients with prednisone-treated exacerbations recover from the impairment associated with this event?

5. When do patients return to their pre-exacerbation state of work/school/physical activity?

E. Primary Research Hypotheses

1. Among asthmatic participants who are persistently non-eosinophilic, the preference for ICS will be greater than placebo.

2. Among asthmatic participants who are persistently non-eosinophilic, the preference for LMA will be greater than placebo.

F. Secondary Research Hypothesis

The differential response to three alternative therapies (ICS, LMA, placebo) will be different in participants with and without airway eosinophilia, as assessed by sputum eosinophils (i.e., asthmatics with airway eosinophilia [sputum eosinophils $\geq 2\%$] will prefer ICS and asthmatics who are persistently non-eosinophilic will prefer LMA).

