The co-primary research hypotheses are that within the non-eosinophilic phenotype, ICS is superior to placebo and LMA is superior to placebo. In statistical terms, the null hypotheses are

- (1) $H_0: p_{Eos-, ICS > Placebo} = p_{Eos-, Placebo > ICS}$
- (2) $H_0: p_{Eos-, LMA > Placebo} = p_{Eos-, Placebo > LMA}$

Since $p_{Eos-,ICS \approx Placebo}$, $p_{Eos-,LMA \approx Placebo}$, $p_{Eos+,ICS \approx Placebo}$, and, $p_{Eos+,LMA \approx Placebo}$ do not factor into the null hypotheses, participants who do not have a differential response (i.e., treatment was equivalent to placebo) will not be included in the analyses. We will apply two-sided, exact binomial tests at the 0.025 significance level (Bonferroni correction) for each of these null hypotheses. To assess potential period and seasonal effects, a sensitivity analysis will be performed by applying logistic regression models to those who had a differential response (i.e., the treatments were not equivalent), with covariates to adjust for period differences, season of enrollment, and ICS delivery (DPI/MDI).

Secondary analyses with the primary outcome include the following:

1. Comparisons within the eosinophilic phenotype in terms of the null hypotheses $H_0: p_{Eos+,ICS > Placebo} = p_{Eos+,Placebo > ICS}$ and $H_0: p_{Eos+,LMA > Placebo} = p_{Eos+,Placebo > LMA}$, which we will test via two-sided, exact binomial tests at the 0.025 significance level (Bonferroni correction) for each of these null hypotheses.
2. Comparisons between the non-eosinophilic and eosinophilic phenotypes in terms of the null hypotheses $H_0: p_{Eos-,ICS > Placebo} = p_{Eos+,ICS > Placebo}$ and $H_0: p_{Eos-,LMA > Placebo} = p_{Eos+,LMA > Placebo}$, which we will test via two-sided, 0.025 significance level Fisher exact tests (Bonferroni correction).
3. Comparison of the ICS and LMA treatments in the manner described above for the primary and secondary analyses (within the non-eosinophilic

phenotype, within the eosinophilic phenotype, and between the eosinophilic and non-eosinophilic phenotypes, respectively).

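### The three-step preference rule names a winner only when regimen A wins a step, which conflicts with the plan's own hierarchy, probabilities and null hypotheses

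*Combined protocol and SAP*

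**What the plan says.** Section VIII.C introduces the rule with "The process is described as follows for the generic comparison of treatment regimen A to treatment regimen B". Its three steps are:

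- **Step 1 (TF).** A wins if TF occurs on B and not on A.
- **Step 2 (ACD).** A wins if it has at least 31 more annualized ACDs than B.
- **Step 3 (FEV1).** A wins if FEV1 is at least 5% better on A than on B.

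When the criterion in step 1 or 2 is met, regimen A "is deemed to be superior to treatment regimen B and the process is terminated. If not, then continue to the next step". Step 3 closes with "If not, then the two treatment regimens are deemed to be" equivalent or tied.

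Other parts of the plan describe what the rule should deliver:

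- Section III.B: "preference to treatment is defined as the following hierarchy of outcomes: Treatment Failure = TF, then Asthma Control Days = ACD", and then FEV1. Section III.H calls the outcome a hierarchical composite, and the sentence in VIII.C that leads into the steps says the comparisons are hierarchical.
- The notation in VIII.C gives placebo wins their own probability, the "probability that placebo is superior to ICS within the non-eosinophilic phenotype", and sets the tie probability to 1 minus the two superiority probabilities.
- The co-primary nulls equate the probability that active is superior with the probability that placebo is superior. Ties are dropped: "participants who do not have a differential response (i.e., treatment was equivalent to placebo) will not be included in the analyses". The test is stated as "We will apply two-sided, exact binomial tests at the 0.025 significance level (Bonferroni correction) for each of these null hypotheses".
- Secondary item 3 in VIII.C reuses the rule: "Comparison of the ICS and LMA treatments in the manner described above for the primary and secondary analyses".

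**The concern.** A hierarchical comparison needs three things at each step: a verdict if A is better, a verdict if B is better, and a move to the next step only if neither is better. The written steps supply the first. For everything else, including a step that B wins, the instruction is to go on, and after step 3 to call a tie.

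This is more than missing detail. A programmer who follows the text exactly gets a definite result, and it is the wrong one for the stated hypotheses. A participant with TF on active only should be a placebo win. In a single pass with A = active, that participant moves to ACD and FEV1 and ends as either an active win or a tie.

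These steps are the only operational definition of the outcome used in both co-primary tests, the tests within the eosinophilic phenotype, the between-phenotype tests and the ICS vs LMA comparisons.

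**Working it through.** **1. The plan's own power figure, and the rule it implies.** Inputs from VIII.G: N = 262, 15% drop-out, 30% ties, difference in win probabilities 0.20, two-sided alpha 0.025.

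- The two win probabilities sum to 1 − 0.30 = 0.70 and differ by 0.20, so they are 0.45 (active) and 0.25 (placebo).
- Among participants with a preference, the active share is 0.45 / 0.70 = 0.643.
- Informative n = 262 × 0.85 × 0.70 = 155.9, about 156.
- Exact two-sided binomial power at n = 156 is 0.9025. Averaged over a random number of ties with 222 evaluable participants it is 0.900. The stated figure is 0.90, so it reproduces.

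This calculation needs placebo to win in 25% of participants, so it presupposes a rule under which placebo can win.

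**2. All component patterns.** Each of the three components can favour active, favour placebo, or show no difference, which gives 3³ = 27 patterns. They are not equally likely, so the counts below describe the rule and not participants.

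*Symmetric rule (the first step with a difference decides, either way).* Active wins at step 1 in 9 patterns, at step 2 in 3 and at step 3 in 1: 9 + 3 + 1 = 13. Placebo wins in 13 by symmetry, and 1 is a tie.

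*Literal rule, one pass, A = active.* Active wins whenever any step favours it: 27 − 2³ = 19. The other 8 are ties. Placebo wins 0.

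The 13 patterns that belong to placebo are reassigned as follows:

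| Step that placebo wins first | Patterns | Become active wins | Become ties |
|---|---|---|---|
| TF | 9 | 5 | 4 |
| ACD | 3 | 1 | 2 |
| FEV1 | 1 | 0 | 1 |
| Total | 13 | 6 | 7 |

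*Literal rule, run once in each order.* A pattern is scored for both regimens whenever at least one step favours each: 27 − 8 − 8 + 1 = 12. Active only: 7. Placebo only: 7. Tie: 1.

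**3. One participant followed through.** TF on ICS only, with at least 31 more annualized ACDs on ICS. With A = ICS, step 1 is not met, step 2 is met, and ICS is superior. With A = placebo, step 1 is met and placebo is superior. The hierarchy in III.B allows only the second verdict.

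**4. Set against the plan.**

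- One pass makes the probability of a placebo win zero by construction. That conflicts with the notation, the nulls and the 0.25 in step 1 above.
- Two passes give overlapping outcomes, so 1 minus the two superiority probabilities is no longer the tie probability.
- Only the symmetric rule gives exclusive outcomes that sum to one and respect TF before ACD before FEV1.

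**5. ICS vs LMA.** Neither regimen is placebo and the plan does not say which one is A. Under the literal single pass, swapping the labels changes the verdict in 26 of 27 patterns: 12 from ICS superior to LMA superior, and 14 between a win and a tie. Section VIII.G nevertheless powers this comparison on wins in both directions. Under the symmetric rule the labels do not matter.

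**The case against.** The strongest reply is that the plan already fixes the meaning. The sentence leading into the steps says the comparison is hierarchical, III.H calls the outcome a hierarchical composite, A and B are generic labels, and the notation defines placebo wins and ties as separate categories. Only a symmetric rule fits all of that, and a table with no placebo wins, or with participants counted twice, would be questioned at once. This stands as evidence of intent and limits the practical risk. It does not repair the steps. Treating the labels as interchangeable produces the double verdicts shown above unless the reader adds that a B win also terminates, and that instruction is the one the text lacks.

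A reader might infer something stronger: that the co-primary tests would almost always reject falsely. With no placebo wins the exact p-value is 2 × 0.5ⁿ, so 7 active wins would reject at 0.025 (p = 0.0156; 6 give 0.031). With no treatment effect and 30% ties, at least 35% of 222, about 78, would be active wins. The arithmetic is right, but it belongs to a reading that the plan's hierarchical language and placebo-win probabilities rule out. It is not a measure of the trial's type I error. Under the symmetric rule the size of the test is 0.020.

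It is also fair to say that pattern counts are not participant effects. The documents give no joint frequency of components that disagree in direction, so the share of participants affected is unknown.

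**Conclusion.** The rule is wrong as written for the primary outcome, and it should be corrected. It is a defect of a stated rule, not a power error: the sample size, test, alpha and stated power all agree with the symmetric rule that the rest of the plan implies.

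The size of the defect is exact as a description of the text. One literal pass misassigns all 13 placebo patterns (6 to active, 7 to tie), and two passes give contradictory verdicts in 12 of 27. These counts assume only that each component has three possible states.

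Two further inferences should be avoided. The text is not silent when B wins a step: its fallback clause covers that case, but sends it on to the next step or to a tie. Nor are the nulls untestable under a single pass: a test could be computed, but it would not address the stated hypotheses. Harm would arise only if the steps were programmed literally and the result went unnoticed.

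**What to change.** Replace the three steps in VIII.C with two-sided, terminating wording:

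1. If TF occurs on exactly one regimen, the other regimen is superior and the process stops. Continue only if TF occurs on both or on neither.
2. If annualized ACDs differ by at least 31 in either direction, the regimen with more is superior and the process stops. Otherwise continue.
3. If FEV1 on one regimen is at least 5% above FEV1 on the other, with the lower value as denominator, the regimen with the higher FEV1 is superior. Otherwise the two are tied.

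Add one sentence stating that the same rule applies to ICS vs placebo, LMA vs placebo and ICS vs LMA.

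The cost is three or four sentences of SAP text before unblinding. No data collection, sample size or patient procedure changes.
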